9.3 Population characteristics

9.3.1 Demographic

Section modified by Amendment 1 (Section 16.1).

The demographic information listed below should be collected for each subject:

- Age
- Ethnicity
- Race
- Employment status
- Number of years of school and professional education
- College / university degree or equivalent professional qualification (yes, no)
- Health insurance (yes, no)
- Substance use
- Alcohol consumption.

9.3.2 Medical history

Medical history findings (i.e., previous diagnoses, diseases, or surgeries) meeting all criteria listed below will be collected as available to the investigator:

- Start before signing of the informed consent;
- Considered relevant for the subject's study eligibility.

Detailed instructions on the differentiation between (i) medical history and (ii) AEs can be found in Section 9.6.1.1.

9.3.3 Other baseline characteristics

Section modified by Amendment 2 ([Modification 19](#)).

- Height / Weight;
- Surgical history;
- Immunologic or allergic / Hypersensitivity history;
- Reproductive and menstrual history;
- Current contraceptive method;
- Current medications;
- Current or history of eyeglasses, body piercings, permanent implants, and body tattoos with metallic colorant;
- Family history, including autoimmune disorders;
- Type of insurance subject is currently using.

9.4 Efficacy

Not applicable.

9.5 Pharmacokinetics / pharmacodynamics

Not applicable.

9.6 Safety

9.6.1 Adverse events

9.6.1.1 Definitions

Section modified by Amendment 1 (Section 16.1) and Amendment 2 ([Modification 4](#), [Modification 20](#), [Modification 21](#), [Modification 22](#), [Modification 23](#)).

Definition of AE

In a clinical study, an AE is any untoward medical occurrence (i.e., any unfavorable and unintended sign [including abnormal laboratory findings], symptom, or disease) in a clinical investigation subject after providing written informed consent for participation in the study. Therefore, an AE may or may not be temporally or causally associated with the use of a medicinal (investigational) device.

A surgical procedure that was planned prior to the start of the study by any physician treating the subject should not be recorded as an AE (however, the condition for which the surgery is required may be an AE).

Adverse device effect (ADE)

An AE related to the use of Essure or medical devices used during laparoscopic sterilization, including AEs resulting from insufficient or inadequate instructions for use, deployment, insert placement, installation or operation or any malfunction of the investigational medical device, use error, or from intentional misuse of the medical device.

In the following differentiation between medical history and AEs, the term “condition” may include abnormal physical examination findings, symptoms, diseases, laboratory, ECG, etc.

- Conditions that started before signing of informed consent and for which no symptoms or treatment are present until signing of informed consent are recorded as medical history (e.g., seasonal allergy without acute complaints).
- Conditions that started before signing of informed consent and for which symptoms or treatment are present after signing of informed consent, at *unchanged intensity*, are recorded as medical history (e.g., allergic pollinosis).
- Conditions that started or deteriorated after signing of informed consent will be documented as adverse events. This includes intercurrent illnesses.

Definition of serious adverse event (SAE)

An SAE is classified as any untoward medical occurrence that, at any dose, meets any of the following criteria (a – g):

- a. Results in death;
- b. Is life-threatening;

The term ‘life-threatening’ in the definition refers to an event in which the subject was at risk of death at the time of the event, it does not refer to an event which hypothetically might have caused death if it were more severe.

- c. Requires inpatient hospitalization or prolongation of existing hospitalization;

A hospitalization or prolongation of hospitalization will not be regarded as an SAE if at least one of the following exceptions is met:

- The admission results in a hospital stay of less than 12 hours;
- The admission is pre-planned (e.g., elective or scheduled surgery arranged prior to the start of the study; admission is part of the study procedures as described in Section 9.2);
- The admission is not associated with an AE (e.g., social hospitalization for purposes of respite care).

However, it should be noted that invasive treatment during any hospitalization may fulfill the criterion of ‘medically important’ and as such may be reportable as an SAE

dependent on clinical judgment. In addition, where local regulatory authorities specifically require a more stringent definition, the local regulation takes precedence.

- d. Requires intervention to prevent permanent impairment or damage;
- e. Results in persistent or significant disability / incapacity;

Disability means a substantial disruption of a person's ability to conduct normal life's functions;

- f. Is a congenital anomaly / birth defect;
- g. Is another serious or important medical event as judged by the investigator.

Medical Device Reporting (MDR) event (incident)

A MDR event is defined as follows: (21 CFR 803 Medical Device reporting)

An event that user facilities become aware of that reasonably suggests that a device has or may have caused or contributed to a death or serious injury; or

- An event that manufacturers or importers become aware of that reasonably suggest that one of their marketed devices:
 - May have caused or contributed to a death or serious injury, or
 - Has malfunctioned and that the device or a similar device marketed by the manufacturer or importer would be likely to cause or contribute to a death or serious injury if the malfunction were to recur.

Unanticipated ADE (UADE)

Any serious adverse effect on health or safety or any life-threatening problem or death caused by, or associated with, a device, if that effect, problem, or death was not previously identified in nature, severity, or degree of incidence in the investigational plan or application or any other unanticipated serious problem associated with a device that relates to the rights, safety, or welfare of subjects.

Device deficiency

Inadequacy of Essure or any other device related to its identity, quality, durability, reliability, safety, or performance, such as malfunction, misuse or use error, and inadequate labeling.

Device malfunction

Failure of Essure or any device to meet its performance specifications or otherwise perform as intended when used in accordance with the US IFU.

Device misuse

A misused Essure or laparoscopic tubal ligation device (used by the investigator in a manner that is contradictory to the US IFU) will not be considered a malfunction.

Device events

Examples include, but are not limited to:

- Device breakage;
- Device deficiency (eg, device malfunction, device misuse);
- Device deployment issue;
- Device kink;
- Device issue;
- Device physical property issue (eg, bent insert, bent catheter tips, catheter coiled, device too flexible, stretched coil).

Device failure

Failure of Essure or laparoscopic tubal ligation device to perform or function as intended, including any deviations from the performance specifications or intended use. For the purposes of this study, an unintended pregnancy that occurs in a subject told to rely on an Essure System for contraception is a device failure.

Important Medical Events

The Important Medical Events list (IME) is developed and published by the European Medicines Agency (<http://eudravigilance.ema.europa.eu/human/textforIME.asp>).

All non-serious AEs reported in this study will be periodically reviewed against the most current IME list. Events that are contained on the IME list will be specifically reviewed and the investigator will be asked to review and confirm whether or not the event meets the criteria for seriousness in his / her opinion. In addition, the following events of special interest will be closely reviewed by the sponsor's study medical expert.

AEs of special safety interest

AEs of special interest are reported in the same time frame as SAEs.

- Unintentional perforations of the uterus, cervix, or fallopian tubes by any surgical instrument or by any sterilization device;
- Expulsion of any sterilization device;
- Device dislocation (devices found in an unintended location);
- Potential new or worsening allergy / hypersensitivity symptoms (e.g., itch [pruritus], rash, hives [urticarial], facial edema, angioedema, allergy to metals, flushing, anaphylaxis), in addition to symptoms that could possibly be related to an inflammatory reaction (e.g., hair loss, fatigue, muscle pain, joint pain, joint swelling);
- Potential new or worsening autoimmune reactions;
- Intraoperative bleeding or complications after undergoing hysteroscopic sterilization with Essure or laparoscopic tubal sterilization, including additional surgical procedures to manage the complications;
- Chronic pelvic pain. Per the definition by the American College of Obstetricians and Gynecologists, chronic pelvic pain is pain in the pelvic area that lasts for 6 months or

longer. In those subjects reporting new or worsening lower abdominal / pelvic pain at any time during the study, either spontaneously or in response to the regularly scheduled PRO tool, evaluation of the event will note if duration of the pain meets this definition.

- Pregnancy (refer to Section 9.6.2);
- Upper genital tract infection (for example, endometritis, salpingo-oophoritis, salpingitis).

Allergic / hypersensitivity reactions

For potential allergic / hypersensitivity reactions, investigators will be instructed that an evaluation should be performed in any subject presenting with urticaria, angioedema, unexplained rash, unexplained itching, flushing, or anaphylaxis. Evaluation will also be performed in subjects who present with other symptoms that could possibly be related to an inflammatory reaction (e.g., hair loss, fatigue, muscle pain, joint pain, joint swelling). This evaluation will include a NiLPT, which is a measure of sensitized T-cell reactivity to nickel in culture; a chromium LPT, which is a measure of sensitization to chromium; serum or plasma nickel level; and serum or plasma titanium level and an inflammatory cytokines panel. For NiLPT and chromium LPT, both the continuous score as well as the positive / negative score (based on established cut-offs for negative responses) will be recorded. The results of these lab tests will be forwarded to the sponsor directly by the central lab and will be made available to the adjudication committee. In addition, any subject presenting with an AE of pelvic / lower abdominal pain and any subject presenting with symptoms she believes are due to a hypersensitivity or allergic reaction will also be evaluated, including a NiLPT, chromium LPT, serum or plasma nickel level, and serum or plasma titanium level and an inflammatory cytokines panel. If removal of a device or any other surgery is performed, pathological evaluation and metallurgic studies (if applicable) will be included. After the evaluation of the subject is complete, regardless of investigator's assessment as to whether or not a hypersensitivity / allergic reaction has occurred, all information will be forwarded to the adjudication committee in a blinded fashion. In cases of pathological evidence, blinding may not be possible. Final determination of whether or not a hypersensitivity / allergic event has occurred will be based on the determination of this committee. Once adjudicated events are available, the following comparisons will be possible:

- Pathological findings (if sufficient specimens are obtained) in subjects with Essure and adjudicated hypersensitivity reactions can be compared to pathological findings in subjects with Essure without hypersensitivity reactions as well as to pathological findings in laparoscopic tubal ligation subjects (with and without adjudicated hypersensitivity reactions).
- Levels of inflammatory markers and HLA type in subjects with Essure and adjudicated hypersensitivity reactions can be compared to corresponding findings in subjects with Essure without hypersensitivity reactions as well as to laboratory results in laparoscopic tubal ligation subjects (with and without adjudicated hypersensitivity reactions). Serum cytokine values will be classified as below the normal range, within the normal range, or above the normal range, as appropriate. These values will be used to provide descriptive summaries of change of categories between baseline and

Year 1 and between baseline and Year 5. For these analyses the safety population will be used to present data by treatment groups and by symptomatic/asymptomatic subjects. Secondary analyses can also be performed in subjects who report positively to events on the Supplementary PRO tools (e.g. fatigue, headache) versus those who do not. These comparisons will not rely on device removal.

- Serum or plasma nickel and titanium levels in subjects with Essure and adjudicated hypersensitivity reactions can be compared to serum or plasma nickel and titanium levels in subjects with Essure without hypersensitivity reactions as well as to serum or plasma nickel and titanium levels in laparoscopic tubal ligation subjects (with and without adjudicated hypersensitivity reactions). Secondary analyses can also be performed in subjects who report positively to events on the Supplementary PRO tools (e.g. fatigue, headache) versus those who do not. These comparisons will not rely on device removal.
- NiLPT and chromium LPT results (both the continuous measurement as well as the positive / negative assessment) in subjects with Essure and adjudicated hypersensitivity reactions can be compared to NiLPT and chromium LPT results in subjects with Essure without hypersensitivity reactions as well as to NiLPT and chromium LPT results in laparoscopic tubal ligation subjects (with and without adjudicated hypersensitivity reactions). Secondary analyses can also be performed in subjects who report positively to events on the Supplementary PRO tools (e.g. fatigue, headache) versus those who do not. These comparisons will not rely on device removal.
- An individual subject's serum or plasma nickel and titanium levels and NiLPT can be compared to baseline levels in order to assess any change. In addition, in cases of removal, subsequent post-removal levels can also be compared.

Autoimmune diseases

For autoimmune disorders, any subject presenting with symptoms indicating a potential autoimmune disorder should be evaluated per standard medical practice. All effort will be made to obtain records of any diagnostic workup conducted by outside physicians. A NiLPT, chromium LPT, serum or plasma nickel level, and serum or plasma titanium level and serum inflammatory cytokines will also be drawn by the study site. An appropriate human leukocyte antigen (HLA) panel will be run on previously obtained baseline samples if sufficient sample exists. An additional whole blood sample will be drawn for HLA if needed. Frozen serum will be used in cases of suspected autoimmune disorders (for both the index case as well as a randomly selected control group). If sufficient frozen sample exists, it will be adequate to be used for tests used to diagnose autoimmune conditions (e.g., anti-citrullinated protein antibody in cases of suspected rheumatoid arthritis, thyroid peroxidase antibody for suspected autoimmune thyroid diseases, and antinuclear antibody in cases of suspected lupus erythematosus). Based on epidemiology, the number of subjects who develop an autoimmune disease during the study is expected to be very small. If removal of a device or any other surgery is performed, pathological evaluation and metallurgic studies (if applicable) will be included.

After the evaluation of the subject is complete, regardless of investigator's assessment as to whether or not an autoimmune disorder exists, all information will be forwarded to the adjudication committee in a blinded fashion. In cases of pathological evidence, blinding may not be possible. Final determination of whether or not an autoimmune disorder has occurred will be based on the determination of this committee. Once adjudicated events are available, the following comparisons will be possible:

- Pathological findings (if sufficient specimens are obtained) in subjects with Essure and adjudicated autoimmune disorders can be compared to pathological findings in subjects with Essure without autoimmune disorders as well as to pathological findings in laparoscopic tubal ligation subjects (with and without adjudicated autoimmune disorders).
- Levels of inflammatory markers and HLA type in subjects with Essure and adjudicated autoimmune disorders can be compared to these findings in subjects with Essure without autoimmune disorders as well as to laboratory results in laparoscopic tubal ligation subjects (with and without adjudicated autoimmune disorders). Secondary analyses can also be performed in subjects who report positively to events on the Supplementary PRO tools (e.g. fatigue, headache) versus those who do not. These comparisons will not rely on device removal.
- Serum or plasma nickel and titanium levels in subjects with Essure and adjudicated autoimmune disorders can be compared to serum or plasma nickel and titanium levels in subjects with Essure without autoimmune disorders as well as to serum or plasma nickel and titanium levels in laparoscopic tubal ligation subjects (with and without adjudicated autoimmune disorders). Secondary analyses can also be performed in subjects who report positively to events on the Supplementary PRO tools (e.g. fatigue, headache) versus those who do not. These comparisons will not rely on device removal.
- NiLPT and chromium LPT results (both the continuous measurement as well as the positive / negative assessment) in subjects with Essure and adjudicated autoimmune disorders can be compared to NiLPT and chromium LPT results in subjects with Essure without autoimmune disorders as well as to NiLPT and chromium LPT results in laparoscopic tubal ligation subjects (with and without adjudicated autoimmune disorders). Secondary analyses can also be performed in subjects who report positively to events on the Supplementary PRO tools (e.g. fatigue, headache) versus those who do not. These comparisons will not rely on device removal.
- An individual subject's serum or plasma nickel and titanium levels and NiLPT can be compared to baseline levels in order to assess any change. In addition, in cases of removal, subsequent post-removal levels can also be compared.

9.6.1.2 Classifications for adverse event assessment

All AEs will be assessed and documented by the investigator according to the categories detailed below.

9.6.1.2.1 Seriousness

For each AE, the seriousness must be determined according to the criteria given in Section 9.6.1.1.

9.6.1.2.2 Intensity

The intensity of an AE is classified according to the following categories:

- Mild;
- Moderate;
- Severe.

9.6.1.2.3 Action taken with study device

Not applicable.

9.6.1.2.4 Treatment(s) of adverse events

Section modified by Amendment 1 (Section 16.1).

- None;
- Remedial drug therapy;
- Additional surgical procedure;
- Change in surgical procedure;
- Other.

9.6.1.2.5 Outcome

- Recovered / resolved;
- Recovering / resolving;
- Recovered / resolved with sequelae;
- Not recovered / not resolved;
- Fatal;
- Unknown.

9.6.1.2.6 Causal relationship

Section modified by Amendment 1 (Section 16.1).

The assessment of the causal relationship between an AE and the sterilization procedure is a decision to be made by the investigator, who is a qualified physician, based on all information available at the time of the completion of the CRF.

Causality should be assessed separately for each procedure as detailed in the CRF. If the investigator feels that the event cannot be firmly attributed to one of the study procedures (e.g. owing to a suspected underlying interaction), the same assessment will be documented for each study procedure.

The assessment is based on the question whether there was a “reasonable causal relationship” to the study procedure or device in question.

Possible answers are “yes” or “no”.

An assessment of “no” would include:

1. The existence of a highly likely alternative explanation, e.g., mechanical bleeding at surgical site.

or

2. Non-plausibility, e.g., the subject is struck by an automobile when there is no indication that the drug caused disorientation that may have caused the event; cancer developing a few days after the first drug administration.

An assessment of “yes” indicates that the AE is reasonably associated with the use of the study procedure or device.

Important factors to be considered in assessing the relationship of the AE to study procedure include:

- Underlying, concomitant, intercurrent diseases: Each event should be evaluated in the context of the natural history and course of the indication being treated and any other disease the subject may have.
- Concomitant medication or treatment: Any drugs the subject is taking or the procedure the subject receives should be examined to determine whether any of them might have caused the event in question.
- Exposure to physical and / or mental stresses: The exposure to stress might induce adverse changes in the recipient and provide a logical and better explanation for the event
- The assessment is not possible.

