Modification 13

Clarification of causal relationship of AEs.

Rationale:

Updated protocol language to reflect that causal relationship of AEs in this study can be related to the procedure or the device.

Sections affected include:

- 9.4.1.2.6 – Causal relationship.

Modification 14

Added the screening question for lower abdominal / pelvic pain and intermenstrual bleeding questions to protocol appendices.

Rationale:

The original protocol did not contain samples of the screening question for lower abdominal / pelvic pain or the two intermenstrual bleeding questions. These were added to the protocol appendices for clarity.

Sections affected include:

- 17.1 – Screening question for lower abdominal / pelvic pain;
- 17.5 – Intermenstrual bleeding questions.

Modification 15

Removed requirement that PRO assessments that occur in conjunction with a study visit must be completed at the study visit.

Rationale:

To make completion of the questionnaires as flexible as possible for subjects, the requirement for the assessments to be completed at the study visit at baseline and 12, 24, and 36 months post procedure has been removed.

Sections affected include:

- 9.2.2.6 – Three months post procedure (phone contact; for laparoscopic group \pm 2 weeks; for Essure group + 2 weeks, once confirmation test results are available);
- 9.2.3.1 – Patient reported outcome data capture system.

Modification 16

Added registration number.

Rationale:

Registration number is now available.

Sections affected:

- Title page.

Modification 17

Corrected description of PROMIS and AMSS screening thresholds.

Rationale:

There was redundant text in the screening threshold description for the PROMIS Scale v 1.0 (Pain Intensity 3a) and incorrect text in the screening threshold description for the AMSS.

Sections affected:

- 9.2.3.4 – Screening Thresholds.

Modification 18

Corrected demographics information.

Rationale:

The collection of tobacco use noted in demographics did not match the CRF.

Sections affected:

- 9.3.1 – Demographic.

Modification 19

Added detail to scoring of inflammatory response and histologic evaluation.

Rationale:

Following an advisory board meeting, it was determined that additional detail and some minor correction was needed for the scoring of inflammatory response and histologic evaluation.

Sections affected:

- 9.4.1.6 – Device removal and surgical pathology.

Modification 20

Corrected text errors.

Sections affected:

- 9.4.3 – Further safety.

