#### **6.5.1 Adverse events**

The subject incidence overall and by MedDRA preferred term within the primary system organ class (SOC) will be shown for the following events:

1. any treatment-emergent AE
2. any treatment-emergent serious AE
3. any study procedure-related treatment-emergent AE (also by specific procedures/devices: related to hysteroscopy, Essure placement, laparoscopy, cauterization/thermal device, Essure insert, clip or ring placement, trochar or veress needle, anesthesia, TVU, HSG, other)
4. any serious study procedure-related treatment-emergent AE (also by specific procedures/devices: related to hysteroscopy, Essure placement, laparoscopy, cauterization/thermal device, Essure insert, clip or ring placement, trochar or veress needle, anesthesia, TVU, HSG, other)
5. any treatment-emergent bleeding event (as reported by investigator)
6. any study procedure-related treatment-emergent bleeding event (as reported by investigator) (also by specific procedures/devices: related to hysteroscopy, Essure placement, laparoscopy, cauterization/thermal device, Essure insert, clip or ring placement, trochar or veress needle, anesthesia, TVU, HSG, other)
7. any treatment-emergent serious bleeding event (as reported by investigator)
8. any treatment-emergent serious study procedure-related bleeding event (as reported by investigator) (also by specific procedures/devices: related to hysteroscopy, Essure placement, laparoscopy, cauterization/thermal device, Essure insert, clip or ring placement, trochar or veress needle, anesthesia, TVU, HSG, other)

9. any treatment-emergent pelvic/abdominal pain event, including both chronic and non-chronic (as reported by investigator)
10. any study procedure-related treatment-emergent pelvic/abdominal pain event, including both chronic and non-chronic (as reported by investigator) (also by specific procedures/devices: related to hysteroscopy, Essure placement, laparoscopy, cauterization/thermal device, Essure insert, clip or ring placement, trochar or veress needle, anesthesia, TVU, HSG, other)
11. any treatment-emergent serious pelvic/abdominal pain event, including both chronic and non-chronic (as reported by investigator)

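### The causality rule gives bleeding at the surgical site as an example of an AE unrelated to the sterilization procedure, so operative bleeding can be undercounted in the procedure-related tables

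*Protocol*

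**What the plan says.** Protocol 9.6.1.2.6 sets the object of the judgement and who makes it: "The assessment of the causal relationship between an AE and the sterilization procedure is a decision to be made by the investigator". The question is whether there was a reasonable causal relationship "to the study procedure or device in question", answered *yes* or *no*. *Yes* means that the AE is reasonably associated with use of the procedure or device. Causality is to be judged separately for each procedure listed in the CRF.

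Two grounds are given for *no*. The first is "The existence of a highly likely alternative explanation, e.g., mechanical bleeding at surgical site". The second is non-plausibility, with examples that speak of a drug, among them "cancer developing a few days after the first drug administration".

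SAP 6.5.1 (Adverse events) builds tables on the answer. Item 3 is "any study procedure-related treatment-emergent AE (also by specific procedures/devices: related to hysteroscopy, Essure placement, laparoscopy" and further categories, including trocar or Veress needle. Item 6 is "any study procedure-related treatment-emergent bleeding event (as reported by investigator", with the same split. Items 4 and 8 are the serious counterparts.

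Protocol 9.6.1.1 lists among the AEs of special safety interest "Intraoperative bleeding or complications after undergoing hysteroscopic sterilization with Essure or laparoscopic tubal sterilization". Protocol 9.2.2.1 has port-site haematoma or bleeding checked before discharge.

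**The concern.** In a drug trial, surgery is a competing cause, and bleeding at a wound is a fair example of an event the drug did not produce. Here the operation is the exposure. Bleeding at its site is among the most direct harms it can cause, yet the protocol uses it to illustrate an unrelated event. The neighbouring drug wording suggests that the list came from a drug-study template. That is an inference, but the study has no study drug.

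At stake are the outputs that attribute harm to a specific procedure or device. An all-bleeding table cannot do this, because it mixes operative bleeding with everything else reported over 60 months. In a study whose stated goal is to assess the safety of the two procedures, the related tables should not rest on an instruction that labels a direct effect of the exposure as unrelated.

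**Working it through.** No figure in the plan is tied to this rule, so there is nothing to reproduce. The check follows one event through the texts.

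1. **The event.** A subject bleeds at the operative site of her index procedure, for example at a laparoscopic port.
2. **The test (Protocol 9.6.1.2.6).** The general definition of *yes* fits, because the bleeding is reasonably associated with the procedure. The first example under *no* also fits, because it names this kind of event. One section supports both answers, so coding can differ between investigators; Protocol 5.1 targets up to 90 sites.
3. **Text that might settle it.** The Amendment 1 log (Protocol 16.1.1) gives the aim of its edit to this section: "Updated protocol language to reflect that causal relationship of AEs in this study can be related to the procedure or the device". I use this as background only. The current text carries that aim in the question and in the definition of *yes*, but the examples under *no* still do not fit it. No SAP section overrides or re-derives the investigator's answer.
4. **Where the answer goes (SAP 6.5.1, Adverse events).**

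| Output | Uses the causality answer? | Event coded *no* is |
|---|---|---|
| Items 1, 2: all AEs, serious AEs | No | counted |
| Items 5, 7: all bleeding, serious bleeding | No | counted |
| Items 3, 4: procedure-related AEs, serious | Yes | lost |
| Items 6, 8: procedure-related bleeding, serious | Yes | lost |
| Special-interest reporting (Protocol 9.6.1.1) | No | reported |
| Main endpoints (SAP 6.4, Tables 2 to 4) | No | unaffected |

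5. **The backstop (Protocol 9.6.1.3).** The sponsor makes its own causality assessment for SAEs only. Protocol 9.6.1.1 exempts a stay under 12 hours from the hospitalization criterion, and Protocol 3.5 says laparoscopic sterilization is often an outpatient procedure. Some operative bleeding may therefore be non-serious and carry only the investigator's answer. Section 9.6.1.3 also describes the sponsor's task in two ways: causality to the study procedure in one place, to the Essure device in another. Under the second, laparoscopic bleeding would have no sponsor causality check. The SAP does not say whose assessment feeds items 4 and 8.
6. **Effect on a comparison.** Let p_E and p_L be the true proportions with procedure-related operative bleeding (Essure, laparoscopic), and f_E and f_L the fractions coded *no* because of the example. The related-bleeding table shows a difference of (1 − f_E)p_E − (1 − f_L)p_L instead of p_E − p_L. The error is f_L·p_L − f_E·p_E. If f is equal in both arms, the difference shrinks by the factor 1 − f and the ratio is preserved. If f differs, the error can go either way. The documents give none of the four quantities.

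**The case against.** The strongest reply is that the rule contains its own corrective. The general test and the definition of *yes* point the right way, and causality is judged procedure by procedure. Bleeding can properly be *no* for the insert or the anaesthesia and *yes* for the trocar. The words *surgical site* could also refer to a later, unrelated operation during follow-up. For SAEs the sponsor looks again. This stands as a limit: the documents do not show that operative bleeding disappears, only that its coding is left ambiguous by an example pointing the wrong way.

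It is also fair that little is hidden. Operative bleeding remains in items 1, 2, 5 and 7, and the special-interest list has no relatedness condition. That list is a safeguard; a reader might see a conflict between it and the causality rule, but it applies whatever the causality answer. The abnormal-uterine-bleeding endpoint is selected by the terms in SAP Table 3. Protocol 10.3 excludes bleeding and pain AEs with another apparent etiology, but neither document ties that step to this yes/no answer. The study is descriptive, with no confirmatory test. All of this stands, and it confines the problem to the procedure-related subset without removing it there.

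**Conclusion.** The concern holds in limited form and should be fixed; it does not threaten the main results. The example contradicts the definition it sits beside, four items in SAP 6.5.1 filter on the answer, and only SAEs have a second look. Operative bleeding can be undercounted in those items, to the extent that investigators follow the example.

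A reader might infer that the related-bleeding table will show 0 v 0 and conceal a real difference. That needs every investigator to follow the example (f = 1 in both arms) and needs rates that the documents do not contain. Purely assumed rates show why no direction can be claimed. Operative-site bleeding of 2% after laparoscopy and 0.5% after Essure would hide 2 − 0.5 = 1.5 points. Uterine bleeding of 5% after hysteroscopy and 1% after laparoscopy would hide 5 − 1 = 4 points the other way. Neither pair has support in the documents, and the all-bleeding tables would still count those events.

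**What to change.** 1. **Protocol 9.6.1.2.6.** Delete the surgical-site-bleeding example and the drug examples. Add: *Bleeding at the operative site of the index procedure is not in itself an alternative explanation to that procedure.* Do not extend this to a presumption of relatedness for perforation, infection or injury, which the example does not mention.
2. **Data already entered.** Version 5.0 is dated 28 June 2022, and Protocol 16.2.1 records that US sale of Essure would end after 31 December 2018. Most index-procedure bleeding has therefore probably been coded already, and this step matters more than the new sentence. List all operative-site bleeding AEs with onset Day 0-30 in both arms, whatever the causality answer, and ask sites to confirm or re-assess under the corrected text. Querying only *no* answers would let counts move in one direction alone. Keep the original answers, and show the related-AE and related-bleeding tables before and after.
3. **SAP 6.5.1 (Adverse events).** State whether the investigator's or the sponsor's assessment feeds the serious procedure-related tables.
4. **Protocol 9.6.1.3.** Reconcile the two descriptions of the sponsor's causality assessment.

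The cost is a short text change, a site letter, one query listing and a second run of the affected tables. Procedure-related counts may change. Re-assessment will be open-label and, for many subjects, years after the event, which is why the original answers should stay visible.
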